1.0 LIST OF ABBREVIATIONS

Abbreviation	Definition
AAV	Adenovirus-associated virus
ABR	Annualized bleeding rate
ADR	Adverse drug reaction
AE	Adverse event
ALP	Alkaline phosphatase
ALT	Alanine transaminase
APTT	Activated partial thromboplastin time
AST	Aspartate transaminase
ATC	Anatomical Therapeutic Chemical
BPV	BioMarin Pharmacovigilance
BU	Bethesda Unit
CRF	Case report form
CSR	Clinical study report
CTCAE	Common Terminology Criteria for Adverse Events (v4.03)
CTL	Cytotoxic T lymphocytes
DRB	Data Review Board
ECG	Electrocardiogram
eCRF	Electronic case report form
EOSI	Events of special interest
ETV	Early termination visit
FAS	Full Analysis Set
FDA	Food and Drug Administration
FVIII	Coagulation factor VIII
FXa	Coagulation factor Xa
GCP	Good Clinical Practice

Proprietary and Confidential Pg. 5 of 38

GGT	Gamma-glutamyl transferase
НА	Haemophilia A
hFVIII	Human coagulation factor VIII
HLA	High Level Term
ICH	International Conference on Harmonisation
IP	Investigational product
IV	Intravenous
LDH	Lactate dehydrogenase
LT	Liver test
LLOQ	Lower limit of quantitation
MedDRA	Medical Dictionary for Regulatory Activities
NAb	Neutralizing antibody
NCI	National Cancer Institute
NOAEL	No-observed-adverse-effect level
PBMC	Peripheral blood mononuclear cells
PD	Pharmacodynamic
PK	Pharmacokinetic
PP	Per-protocol
PRO	Patient reported outcome
PT	Preferred term
Qol	Quality of life
rhFVIII	Recombinant human FVIII protein
SAE	Serious adverse event
SAP	Statistical analysis plan
SD	Standard deviation
SDTM	Study Data Tabulation Model
SE	Standard error

Proprietary and Confidential Pg. 6 of 38

SFU	Spot-forming units
SOC	System organ class
TAb	Total antibody
TEAE	Treatment-emergent adverse event
TI	Transduction Inhibition
TLGs	Tables, listings, and graphs
vg	Vector genomes
WHO	World Health Organization

2.0 INTRODUCTION

This document describes the statistical methods to be implemented in the analysis of data collected under clinical study protocol 270-201, "A Phase 1/2, Dose-Escalation Safety, Tolerability and Efficacy Study of BMN 270, an Adenovirus-Associated Virus Vector-Mediated Gene Transfer of Human Factor VIII in Patients with Severe Haemophilia A" (Amendment 8, 31 January 2019). The SAP contains definitions of analysis populations, derived variables, and statistical methods for the analyses of efficacy and safety.

2.1 Study Overview and Objectives

BMN 270 is an AAV5-based gene therapy vector that expresses the SQ form of hFVIII under the control of a liver-selective promoter. BMN 270 will be delivered by single intravenous dose and is designed to achieve stable, potentially life-long expression of active hFVIII in the plasma, synthesized from vector-transduced liver tissue. The clinical study 270-201 is a first-in-human study designed to assess the relationship of vector dose to the augmentation of residual FVIII activity and whether these levels are sufficient to alter the clinical phenotype. The relationship of dose to safety will be correlated to the activity of hFVIII in subjects with severe HA.

The primary objectives of the study are:

- To assess the safety of a single intravenous administration of a recombinant AAV5 encoding human coagulation FVIII (AAV5-hFVIII-SQ) vector.
- To determine the dose of AAV5-hFVIII-SQ required to achieve FVIII at or above 5% of normal activity (\geq 5 IU/dL) at 16 weeks after infusion. The kinetics, duration, and magnitude of AAV-mediated FVIII activity in individuals with haemophilia A will be determined and correlated to an appropriate BMN 270 dose.

The secondary objectives of the study are:

- To describe the immune response to the FVIII transgene product and AAV capsid proteins following systemic administration of AAV5-hFVIII-SQ.
- To assess the impact of BMN 270 on the frequency of FVIII replacement therapy during the study.
- To assess the impact of BMN 270 on the number of bleeding episodes requiring treatment during the study.

2.2 Study Design

This is a first-in-man, phase 1/2 open-label, dose escalation study in subjects with severe haemophilia A. Eligible subjects will enter the dose escalation part of the study, followed by a 16-week Post-Infusion Follow-Up period during which safety and efficacy assessments will be taken. After the primary endpoint analysis at 16 weeks, safety and efficacy will then be assessed for approximately 5 years.

Subjects who provide written informed consent, meet the entry criteria definition of severe HA, and do not have transduction inhibition activity to AAV5 will be eligible to enroll in the study. Participants will be enrolled into one of up to four cohorts according to dose level as a single intravenous (IV) infusion:

Cohort 1: 6E12 vector genomes [vg] per kilogram of body weight

Cohort 2: 2E13 vg per kilogram

Cohort 3: 6E13 vg per kilogram Cohort 4: 4E13 vg per kilogram

The starting dose was based on the expression and safety of FVIII observed in nonclinical studies of mice and monkeys. The starting dose has a significant safety margin (10-fold) from no observed adverse effect level (NOAEL) in mice.

Cohort 1-3

The first 3 cohorts will be enrolled sequentially, allowing a period of 3 weeks or more between cohorts. Dose escalation may occur after a single subject in a cohort has been safely dosed if the resulting FVIII activity at the Week 3 visit is < 5 IU/dL in both the one-stage clotting and chromogenic substrate assays. If the FVIII activity reaches ≥ 5 IU/dL at the Week 3 visit and no safety issue is found, then the remaining subjects in the cohort will be enrolled without the need to wait for 3 weeks between subjects. The flow chart of dose escalation scheme for Cohorts 1 to 3 is shown in Figure 2.2.1. Three weeks is expected to be the time the expression will be close to the maximum. This escalation paradigm is intended to minimize the subject numbers exposed to subtherapeutic doses. The decision to escalate to the next dose level will be made based on the review of safety parameters and FVIII activity by the Sponsor and a panel of investigators participating in the study.

Patient 1: 6E12 Optimum number of patients per dose: ≥ 5% <5% Patient 2-4: 6E12 Patient 2: 2E13 2E13 N=1-4 N=4+ ≥ 5% <5% Patient 5-8: 2E13 Patient 3-5: 2E13 Patient 3: 6E13 <5% ≥ 5% Stop

Figure 2.2.1: Flow Chart of Dose Escalation Scheme for Cohorts 1 to 3

Cohort 4

For Cohort 4, 3 subjects will be enrolled at 4E13 vg/kg. If FVIII activity in these 3 subjects is \geq 5% at 8 weeks and if no safety issue is found, an additional 3 subjects may be enrolled in this cohort.

All Cohorts

There will be an ongoing review of individual subject safety and efficacy data by the medical monitor and

Proprietary and Confidential Pg. 9 of 38

the DRB. The adaptive nature of this trial allows the DRB to recommend allocating subjects to the cohorts based on activity levels of FVIII and safety signals.

Because subjects develop neutralizing immunity upon exposure to the AAV5 capsid, re-challenge of vector is not a likely treatment option, and these subjects have effectively a single opportunity for therapy using this AAV capsid. Efficacy will be determined by FVIII activity at 16 weeks post-dose. Safety will be evaluated for approximately 5 years after dosing. Any safety signal may trigger a review of the data and possible additional immunogenicity studies that include an assessment of cellular immune responses using collected peripheral blood mononuclear cells (PBMC). Additionally, if any of the events listed in protocol Section 9.3.4.1 occur, enrollment into the trial will be halted to complete an extensive safety analysis. Notification of the study enrollment halt will be sent by the Sponsor to the participating sites via telephone and email immediately after becoming aware of a safety concern. This will ensure no additional subjects are dosed until the signal has been completely evaluated. If, following safety review by the DRB and the Sponsor, it is deemed appropriate to restart dosing, a request to restart dosing with pertinent data will be submitted to the health authority.

2.3 Study Population

Subjects eligible to participate in this study must meet all of the following inclusion criteria:

- Males that are 18 years or older with established severe haemophilia A as evidenced by their medical history. Subjects will be considered as severe if their base FVIII level is 1 IU/dL or less
- Treated/exposed to FVIII concentrates or cryoprecipitate for a minimum of 150 exposure days (EDs)
- Greater or equal to 12 bleeding episodes only if on on-demand therapy over the previous 12 months. Does not apply to subjects on prophylaxis
- Able to sign informed consent and comply with requirements of the trial
- No history of inhibitor, and results from a modified Nijmegen Bethesda assay of less than 0.6
 Bethesda Units (BU) on 2 consecutive occasions at least one week apart within the past 12
 months
- Sexually active subjects must be willing to use an acceptable method of contraception such as
 double barrier, including hormonal contraception for at least 6 months post treatment. After 6
 months, subjects may stop contraception use only if they have had 3 consecutive negative semen
 samples.

Subjects are not eligible for this study if they meet any of the following exclusion criteria:

- Detectable pre-existing immunity to the AAV5 capsid as measured by AAV5 transduction inhibition or AAV5 total antibodies
- Any evidence of active infection or any immunosuppressive disorder.
- HIV positive

Proprietary and Confidential Pg. 10 of 38

- Significant liver dysfunction as defined by abnormal elevation of:
 - o ALT (alanine transaminase) to 3 times the upper limit of normal;
 - o Bilirubin above 3 times the upper limit of normal;
 - o Alkaline phosphatase above 3 times the upper limit of normal; or
 - o INR (international normalized ratio) ≥ 1.4
- Potential participants who have had a liver biopsy in the past 3 years are excluded if they had significant fibrosis of 3 or 4 as rated on a scale of 0-4
- Evidence of any bleeding disorder not related to Haemophilia A
- Platelet count of $< 100 \times 10^9/L$
- Creatinine $\geq 1.5 \text{ mg/dL}$
- Liver cirrhosis of any etiology as assessed by liver ultrasound
- Hepatitis B if surface antigen is positive
- Hepatitis C if RNA is positive
- Treatment with any IP within 30 days prior to the end of the screening period
- Any disease or condition at the physician's discretion that would prevent the patient from fully
 complying with the requirements of the study including possible corticosteroid treatment outlined
 in the protocol. The physician may exclude subjects unwilling or unable to agree on not using
 alcohol for the 16-week period following the viral infusion.
- Prior treatment with any vector or gene transfer agent
- Major surgery planned in the 16-week period following the viral infusion
- Use of immunosuppressive agents or live vaccines within 30 days before the viral infusion

2.4 Study Dosage and Administration

Each subject will receive a single IV injection of BMN 270 as an intravenous infusion. The volume of infusion will depend on the dose level:

- 1. 6E12 vector genomes [vg] per kilogram of body weight
- 2. 2E13 vg per kilogram
- 3. 6E13 vg per kilogram
- 4. 4E13 vg per kilogram

2.5 Sample Size Determination

No formal sample size calculations based on statistical power were performed. The sample size is determined based upon clinical considerations and the ability to detect a strong clinical efficacy signal.

Proprietary and Confidential Pg. 11 of 38

Up to 15 subjects may be dosed in the study. The actual number of subjects will depend on the criteria for dose escalation.

2.6 Blinding and Randomization Methods

2.6.1 Blinding Method

Study 270-201 is an open-label study. No blinding will be performed.

2.6.2 Randomization Method

Study 270-201 is a dose escalation study. No randomization will be performed.

2.6.3 Interim Analysis

No formal interim analysis is planned. An analysis of the primary endpoint will be done following all subjects having completed the study assessments through the end of the Post-Infusion Follow-Up Period (Week 16).

3.0 GENERAL ANALYSIS CONSIDERATION

The subjects will be followed in a longitudinal manner, and all relevant information will be collected. The analysis of the data will be descriptive in nature. Descriptive statistics include subject count, mean, median, standard deviation, coefficient of variation, minimum, and maximum for continuous variables and count and percentage for categorical variables. The 95% confidence interval (CI) for the mean and the percentiles may also be included, if appropriate. Safety and efficacy variables will be summarized by dose cohort, and safety and efficacy results related to dose levels will be examined. Data collected in a longitudinal manner may be analyzed using longitudinal methods, such as mixed effect models, which take into account the correlation among the observations taken at various time points within a subject. Subgroup analyses may be performed, if appropriate.

3.1 Analysis Populations

3.1.1 Efficacy

The primary analysis population for efficacy analyses is the Full Analysis Set (FAS), defined as all enrolled subjects who receive BMN270 infusion and have at least one Baseline and post-Baseline assessment. The FAS will be used for efficacy analysis.

When applicable, additional efficacy sensitivity analyses will be carried out for the Per-Protocol (PP) analysis population, defined as a subset of the FAS who are compliant with the protocol and do not have major protocol violations that affect the interpretability of efficacy data. The PP population will be determined by team data review; reasons for excluding subjects will be defined and documented.

3.1.2 Safety

The Safety Analysis Population is defined as all enrolled subjects who receive BMN270 infusion. The analysis of safety data will be performed on Safety Analysis Population.

Proprietary and Confidential Pg. 12 of 38

3.2 Treatment Group Presentation

In general, statistical summaries for each endpoint will be presented by BMN 270 dose levels subjects were assigned to (eg, 6E12 vg/kg, 2E13 vg/kg, 4E13 vg/kg, 6E13 vg/kg) and overall.

3.3 Study Day Derivation

Study day is assigned as follows:

- The study drug infusion date is designated as Day 1.
- For visit days after Day 1, study day = visit date Day 1 date + 1.
- For visit days prior to Day 1, study day = visit date Day 1 date (Thus, study days for screening visits are negative numbers.)

3.4 Visit Windows for Analysis

Efficacy and safety data will be summarized by visit or by combining multiple visits based on windows defined in terms of study days, wherever applicable. Assessments will be assigned to derived visits according to the window into which the study day falls (Appendix 17.1). Unless stated otherwise, if there are two or more assessments within a designated window, the assessment that is closest to the target day will be used for analyses. If the two closest assessments to the target day are equidistant from the target day, then the mean of the two assessments will be used for analyses unless otherwise specified. If FVIII activity level is retested, the retest assessment will be used for the analyses.

3.5 Handling of Dropouts and Missing Data

If a subject withdraws from the study prior to the Week 260 visit, the subject will be asked to complete an Early Termination Visit (ETV).

Missing dates or partially missing dates will be imputed conservatively for concomitant medications and adverse events (AEs) to ensure that an AE is considered treatment emergent and the duration is the longest possible duration.

FVIII activity levels below the LLOQ (Lower limit of quantitation) will be imputed with 0 IU/dL.

Missing data will not be imputed unless otherwise stated. The main analyses will be observed cases (no imputation), in some cases supported by repeated measures approaches.

4.0 SUBJECT DISPOSITION

The number of subjects screened, number and percentage of screen failures by screen failure reasons will be summarized for all subjects screened. The number of subjects enrolled and the number and percentage by reason for subjects enrolled but not treated will be provided.

5.0 DISCONTINUATION AND COMPLETION

For treated subjects who prematurely discontinue study participation prior to the Week 26 visit, prior to the Week 52 visit and overall, the primary reason for discontinuation will be summarized by dose cohort.

Proprietary and Confidential Pg. 13 of 38

The number and percentage of subjects who are continuing the study, who completed Week 104, and who completed Week 156 will also be provided for all treated subjects overall and by dose cohort.

6.0 PROTOCOL DEVIATIONS

The trial's Study Specific Guideline for Managing Protocol Deviations defines protocol deviations, including whether they are minor or major. Major protocol deviations will be summarized overall and by category for each dose cohort. A data listing of protocol deviations will be provided as well.

7.0 DEMOGRAPHICS AND BASELINE CHARACTERISTICS

Subject demographic and baseline characteristics to be summarized include

- age at enrollment (year)
- age group (>=18-<30,>=30-<50,>=50)
- sex (Female/Male)
- ethnicity
- race
- height (cm)
- weight (kg)
- BMI (kg/m²)
- Baseline ECG evaluation
- history of liver disease (Yes/No)
- history of hepatitis B (Yes/No)
- history of hepatitis C (Yes/No)
- history of HIV (Yes/No)
- baseline disease characteristics including:
 - o time since diagnosis of hemophilia A (year)
 - o type of FVIII treatment for hemophilia A (prophylaxis/on demand)
 - o history of FVIII inhibitor (Yes/No)
 - number of target joints
 - o body location of target joints
 - ambulatory assist device requirement (Yes/No)
- baseline FVIII activity (IU/dL)
- duration of baseline data collection periods, months
- baseline annualized utilization (IU/kg/year) of exogenous FVIII replacement therapy
- baseline annualized number of FVIII infusions (infusions/year)

Proprietary and Confidential Pg. 14 of 38

• baseline ABR (bleeds/year)

8.0 MEDICAL HISTORY

Medical history will be coded using the most current version of Medical Dictionary for Regulatory Activities (MedDRA) at the time of coding. Medical history will be summarized by system organ class (SOC) and preferred term (PT).

9.0 PRIOR AND CONCOMITANT MEDICATIONS/PROCEDURES

Prior and concomitant medications are defined as follows:

- prior medication—any medication taken prior to the initiation of the investigational product and within 30 days prior to screening;
- concomitant medication—any medication taken after the initiation of the investigational product.

When a medication starts prior to the initiation of the investigational product and continues while on study, it will be summarized as both prior and concomitant medications.

All medications will be coded using the current version of the World Health Organization Drug (WHO Drug) Dictionary.

Prior and concomitant medication use will be separately summarized by Anatomical Therapeutic Chemical (ATC) medication class (Level 4) and preferred name (i.e., generic medication name). A subject reporting the same medication more than once will be counted once when calculating the number and percentage of subjects who received that medication.

Corticosteroid usage including total dose and total duration per subject, dose per use, duration per use, and time to corticosteroid use will be summarized overall and by for therapeutic and prophylactic purposes.

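### Read literally, the prior-medication window closes at screening and the concomitant window opens at infusion, so a drug both started and stopped in between falls in neither summary

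*SAP*

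**What the plan says.** SAP Section 9.0 sets two categories. A prior medication is "any medication taken prior to the initiation of the investigational product and within 30 days prior to screening". A concomitant medication is "any medication taken after the initiation of the investigational product". A carry-over sentence then deals with a drug begun before the investigational product and still being taken on study: "it will be summarized as both prior and concomitant medications". These are the only two categories tabulated: "Prior and concomitant medication use will be separately summarized by Anatomical Therapeutic Chemical (ATC) medication class".

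Two other places show that screening and infusion are separate points in time. Section 3.3 notes that "study days for screening visits are negative numbers", with the infusion on Day 1. An exclusion criterion in Section 2.3 reads "Treatment with any IP within 30 days prior to the end of the screening period", so screening is itself a period with an end. The SAP does not state how long the interval from screening to infusion is.

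**The concern.** Under the literal reading of the prior-medication definition, both conditions must hold: use before infusion, and use in the 30 days before screening. The concomitant definition begins only at infusion. Nothing covers the time between, except for drugs that carry on past the infusion.

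That interval comes immediately before a single gene transfer. Short courses taken then are useful background when infusion-related reactions (Section 12.1.5) and liver tests (Section 12.2) are read. A program that applies the definition as written would leave those courses out of both medication summaries without any warning. Because the definition and the carry-over sentence disagree, two programmers could also classify the same drug differently.

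**Working it through.** The SAP gives no figure to reproduce here, so the check is to apply the rules to each possible timing of a course.

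**Inputs**
- Prior: taken before infusion and within the 30 days before screening (Section 9.0).
- Concomitant: taken after infusion begins (Section 9.0).
- Carry-over: begun before infusion and continuing on study counts as both (Section 9.0).
- Screening precedes Day 1 (Section 3.3). The length of the interval, S days, is not in the SAP and is assumed.

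**Classification by timing**

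| Course of drug | Prior, as written | Concomitant | Carry-over sentence | Result |
|---|---|---|---|---|
| Used in the 30 days before screening, stopped before infusion | Yes | No | Does not apply | Prior |
| Started and stopped between screening and infusion | No | No | Does not apply | Neither |
| Given on Day 1 before the infusion starts, not continued | No | No | Does not apply | Neither |
| Started between screening and infusion, continued past infusion | No | Yes | Both | Definition and carry-over conflict |
| Started after infusion | No | Yes | Does not apply | Concomitant |
| Stopped more than 30 days before screening | No | No | Does not apply | Neither, as intended |

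The second and third rows are the gap. The fourth is the internal conflict.

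**Does the gap depend on the interval's length?** Count the whole-day courses that start on or after the screening day and stop by the day before infusion. With S days available there are S(S + 1)/2 of them.

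| S (assumed) | Courses | In neither summary, as written | In neither summary, window extended to infusion |
|---|---|---|---|
| 7 | 7 × 8 / 2 = 28 | 28 | 0 |
| 14 | 14 × 15 / 2 = 105 | 105 | 0 |
| 28 | 28 × 29 / 2 = 406 | 406 | 0 |
| 42 | 42 × 43 / 2 = 903 | 903 | 0 |

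The literal rule misses every course confined to the interval, whatever its length, and a window that runs up to infusion misses none. The table counts only courses confined to the interval. It therefore tests the rule and the repair, and does not measure how often such courses occur.

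**The case against.** The strongest reply is that the literal reading is not the natural one. Screening always precedes infusion, so if the prior window closed at screening, the words about the investigational product would add nothing. Both clauses do some work only if the look-back opens 30 days before screening and use may run up to infusion. The carry-over sentence supports this, because it treats infusion as the boundary for prior use. This argument stands as to intent: the broader meaning was probably meant. It does not remove the point, because an analysis plan has to fix the date condition, and the one it prints differs from the one it probably means.

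A reader might also infer more than the SAP supports:

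- *That all use in the interval is lost, for all of the up to 15 subjects.* Drugs used in the 30 days before screening and stopped in the interval still count as prior, and drugs continuing past infusion are captured. The SAP gives no ground for saying that any subject had a course confined to the interval.
- *That the interval is at least about a week, because the baseline visit is set at Day -7 to Day -1.* Appendix 17.1 allows that visit as late as Day -1, so no one-week minimum follows.
- *That a breach of an exclusion would be hidden and the per-protocol set affected.* One criterion is "Use of immunosuppressive agents or live vaccines within 30 days before the viral infusion", which counts back from infusion. But per-protocol membership is decided by team data review with documented reasons (Section 3.1.1), and deviations are summarised and listed on their own (Section 6.0). Neither relies on the prior-medication table. Nor is it a contradiction that an eligibility look-back counts from infusion while a descriptive one counts from screening.
- *That no summary would show such exposure.* Section 9.0 summarises corticosteroid use separately, without limiting it to either category. FVIII use before Day 1 falls in the baseline window of Appendix 17.1, and FVIII use on Day 1 in the Week 1-4 window.

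**Conclusion.** The point holds as a defect of wording with a narrow effect. Read literally, the two definitions leave a drug both started and stopped between screening and infusion in neither summary, and the prior definition conflicts with the carry-over sentence beside it. What can be lost is short courses confined to that interval, from descriptive medication tables only. No endpoint, estimate, test or per-protocol decision depends on the rule. The number of records affected cannot be derived from the SAP, since it gives neither the length of the interval nor any information on drug use within it. The conclusion that the gap exists rests only on the text of Section 9.0 and on screening coming before Day 1. It is a minor correction, worth making because the printed rule would omit records if programmed as it stands.

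**What to change.** In Section 9.0, replace the definition of prior medication with: *any medication taken at any time from 30 days before screening up to the start of the BMN 270 infusion*. Leave the concomitant definition and the carry-over sentence as they are. This closes the gap and removes the conflict, because a drug started after screening and continued past infusion then meets both definitions directly.

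The cost is one sentence in the SAP and one date condition in the medication program. The prior-medication table may become slightly longer. Flagging, in a listing, any immunosuppressant or live vaccine taken in the 30 days before infusion is optional and is not needed to close the gap.
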